We will also obtain a 4ml K_3 EDTA blood sample just prior to the Dose 1 drug administration on Day 3 to assess our trough level and another 4ml K_3 EDTA blood sample on Day 3 at 15 min (\pm 5 min) after the Dose 1 drug administration to assess our peak level In total, for the whole study duration, the maximum amount of blood that could be collected for the purpose of this study and in addition to the usual routine of medical care of care blood drawn is about 3.5 tablespoons. Peak and trough levels can also be obtained +/- one day to accommodate potential weekend blood draws.

Treprostinil or Placebo Administration:

Subjects will be treated using the Tyvaso® TD-100 Inhalation System. Oxygen will be delivered by nasal cannula or high flow nasal oxygen delivery system. Patients will be managed by an Oxygen Titration Protocol (See Appendix 3). Ampules of either active drug or saline (placebo) will be stored in blinded foil packs prepared and dispensed from Investigational Drug Services. Each will be labeled with a specific identifier that correlates with the randomization scheme. Once randomization occurs, the study coordinator will obtain the appropriate foil pack from IDS. The respiratory therapist will load the ampule into the TD-100 system. Remaining ampules will be stored in the foil pack to protect from light. The respiratory therapist will oversee the subject's administration of the drug, including the counting of the number of breaths taken. One ampule of drug will deliver 24 hours of medication or placebo. Ampules will be replaced every 24-hour period. On Study Day 00, during the Dose Escalation Phase, a blood pressure will be checked prior to Dose 1 and within 30 minutes after; prior to Dose 3 and within 30 minutes after; prior to Dose 5 and within 30 minutes after, or after a different dose interval, if the study drug had to be maintained due to an adverse effect. Blood pressure measurements for Study Days 01 through 11 will be captured from the nursing flow-sheets. The coordinators should document the blood pressure that was recorded as close as possible prior to the Dose 1 time frame for each study day. Arterial blood gas, systemic BP measurements, and central venous O2 saturation (if a CVC is in place) will be checked according to the schedule below (Table 2). Biomarker levels will be checked on Day 0, 3 and 7 as per Table 2.

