NOTE: A study day is defined as 24hrs from Randomization, not calendar days. The study calendar window will start with Day 0.

The following dosing schedule will be utilized*:

Dosing Schedule

Version: 02-09-2018

Time following	Number of
Randomization	Breaths
Dose Escalation Phase	
T= 0 Initial Dose	6
T= 4 hours	6
T= 8 hours	9
T= 12 Hours	9
T= 16 hours	12
Maintenance Dose Phase	
T= 20 hours Thru	
Day 7	12
•	
Taper Down Phase	
Day 8 q 6 hours	12
Day 9 q 6 hours	6
Day 10 q 6 hours	4
Day 11 q 6 hours	2
Day 12 Off Drug	

If an increase in dose (during the Dose Escalation Phase) is not tolerated due to worsening hypoxemia, hypotension, or excessive coughing, the subject will be maintained at the previous dose for an additional 4 hours (unless major adverse events leading to premature withdrawal are noted as defined below). If a dose increase (during the Dose Escalation Phase) is again not tolerated the subject will remain on the highest tolerated dose for the remainder of the 7 day treatment period. During the Dose Escalation Phase, a sustained decrease of mean arterial blood pressure (MAP) by 15% or below MAP 65 will result in a decrease of dose to the previous tolerated level. Transient worsening hypoxemia is defined as a decrease in SPO₂ of 7% or more within 15 minutes of treatment for no longer than 15 minutes not associated with coughing or exertion.

If subject develops worsening oxygenation (as defined by need to increase supplemental oxygen to $> 0.50 \; \text{FiO}_2$) at any point in the Taper Down Phase, then dose should be increased to previously tolerated dose that resulted in acceptable oxygenation. Subject should be maintained at that dose for 24 hours and attempt to taper drug downward again should be made. If subject still cannot be tapered downward, then subject will transition out of the trial and consideration given to transition to inhaled lloprost (UNC Hospital formulary inhaled prostacyclin) or epoprostenol.

The Taper Down Phase will begin prior to Day 8 for patients who are able to maintain an arterial oxygen saturation of >90% on room air or for patients for who discharge to home on oxygen is anticipated. If there is a plan to discharge to home, the patient's current dose of inhaled

Version: 02-09-2018

treprostinil or placebo will be reduced by one-half on the day prior to anticipated discharge, and then discontinued on the day of discharge home.

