Cough or pharyngitis may occur with the administration of inhaled treprostinil. It is usually mild. The investigator may choose to utilize conservative measures such as topical throat lozenges/spray or non-narcotic based antitussive medications to improve compliance with drug administration.

All enrolled patients will receive standard medical care for their acute presenting illness regardless of randomization group, including but not limited to: antibiotics, IV fluids, supplemental oxygen, and any other needed diagnostic testing or imaging.

*Premature Withdrawal from Treatment:

The following adverse effects should prompt cessation of study drug:

- 1. A drop in oxygen saturation by >/= 10 percentage points, to an absolute value of < 90%, within 15 minutes of drug administration, regardless of apparent relationship to coughing.
- 2. Severe, intractable cough resulting in worsening hypoxemia and prolonged increase in O₂ requirement (Defined as an increase of more than 2LPM O₂ that closely correlates temporarily with the cough.)
- 3. Systemic hypotension requiring increase in vasopressor dose or initiation of vasopressors due solely to the administration of study drug (i.e. not due to underlying illness such as septic shock, as determined per the discretion of the investigator) despite titrating down to previously tolerated level.
- 4. Intubation and mechanical ventilator support
- 5. Need for Bi-level Positive Airway Pressure (BiPAP) or Continuous Positive Airway Pressure (CPAP) via face mask for worsening hypoxemia.

These patients will be followed out to study completion as defined by death, 28 days from randomization, or hospital discharge whichever comes first. Discharged subjects will receive a 28 day post randomization phone assessment of disease outcomes and adverse events.

Completion of Study Drug Administration:

Patients will be considered to have completed the study drug administration portion of the study and the study drug will be stopped when one of the following conditions is met, whichever comes first:

- 1. Up to 12 days after randomization (maximum treatment period)
- 2. Discharge from study hospital. Subjects will receive a 28 day post randomization phone assessment of disease outcomes and adverse events.

3. Death

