SBP / MAP (if arterial line is in place otherwise cuff)	Х	х	х	х	х	х	х	х						
Adverse Events Review	х	х	х	х	х	х	х	х	х	х	х	х		
Hospital Mortality														х
Phone Assessment of Disease Outcomes and Adverse Events														х
Day 28 Mortality														Х

Version: 02-09-2018

Appendix 3

Oxygen Titration Protocol

The goal of the Oxygen Titration Protocol is to maintain a resting oxygen saturation of 90-94%. Brief increases in the research subject's O₂ liter flow for ambulation and exertion can be allowed. However, before each study drug administration, the respiratory therapist should make sure that the research subject is on the lowest amount of oxygenation required to achieve an oxygen saturation of 90-94% before recording their baseline O₂ requirement. Reassessment of oxygen saturation before and after each level should occur. Research subjects will start with a conventional humidified nasal cannula. If oxygen titration is needed, we will titrate from their current nasal cannula flow rate in the following stepwise fashion: 4LPM / 5LPM /6LPM. If there is a need for oxygen titration above 6 LPM, we will utilize a High Flow Nasal Cannula with the flow rate of 20 to 50 LPM. We will titrate the High Flow Nasal Cannula FiO2 in the following stepwise fashion: 50%, 60%, 70%, 80%, 90%, and 100%. The required liter flow will be titrated per patient need/demand. If a patient requires more than 50LPM via HFNC, they will have met our classification of *requiring positive pressure threshold*. If clinically indicated, clinicians that are managing the care of these research subjects can initiate non-invasive ventilation or proceed to intubate prior to a patient reaching 100% O₂ or 50LPM flow rate, per our stepwise fashion.

FiO₂ Conversion Table

FIU ₂ Con	version rable
Conventional Humidified Nasal Cannula Flow Rate	FiO ₂
1 LPM	24%
2 LPM	28%
3 LPM	32%
4 LPM	36%
5 LPM	40%
6 LPM	44%
High Flow Nasal Cannula Flow Rate	FiO ₂
20 LPM to 50LPM	50%
20 LPM to 50LPM	60%
20 LPM to 50LPM	70%
20 LPM to 50LPM	80%
20 LPM to 50LPM	90%
20 LPM to 50LPM	100%
	1

Version: 02-09-2018

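### The dose cap for patients who fail escalation ends after the 7-day treatment period, and the printed Day 8 taper dose is then at or above the dose they could not tolerate

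*Combined protocol and SAP*

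**What the plan says.** All of this is in the combined protocol and SAP, mostly in the Dosing Schedule under Treprostinil or Placebo Administration.

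- **Escalation.** Doses step through 6, 9 and 12 breaths at 4-hour intervals. After a first increase that is not tolerated (hypoxemia, hypotension or cough), the patient stays at the previous level for 4 more hours. If an increase fails again, "the subject will remain on the highest tolerated dose for the remainder of the 7 day treatment period".
- **Taper.** The Taper Down rows give 12, 6, 4 and 2 breaths every 6 hours on Days 8, 9, 10 and 11, and no drug from Day 12. No row depends on the level the patient tolerated.
- **Early taper.** "The Taper Down Phase will begin prior to Day 8 for patients who are able to maintain an arterial oxygen saturation of" more than 90% on room air, and for patients expected to go home on oxygen. The text does not say which row they enter.
- **Worsening oxygenation in the taper.** If the oxygen need passes an FiO₂ of 0.50, "then dose should be increased to previously tolerated dose that resulted in acceptable oxygenation".
- **Planned discharge home.** The current dose is halved the day before and stopped on the day of discharge.
- **Blood pressure.** The dose-reduction rule opens "During the Dose Escalation Phase, a sustained decrease of mean arterial blood pressure (MAP) by 15% or below MAP 65". Readings before and after a dose are specified for Study Day 0 only; after that, "Blood pressure measurements for Study Days 01 through 11 will be captured from the nursing flow-sheets".
- **Duration.** Completion of Study Drug Administration sets the maximum treatment period at up to 12 days.

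**The concern.** The cap exists because the patient has shown that the next dose level is not tolerated. It lapses at the point where the table prints the full 12-breath dose. A respiratory therapist who follows the Day 8 row would give a capped patient four doses that day, each above the tolerated single dose.

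The other patient-specific rules do not cover this case. Halving applies only to planned discharge home. The return to a tolerated dose is triggered by worsening oxygenation and moves the dose up. Criterion 3 of Premature Withdrawal from Treatment mentions down-titration ("despite titrating down to previously tolerated level") only once hypotension has occurred, and it stops the drug only if vasopressors are started or increased.

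Protection during the taper is uneven:

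- **Oxygen.** Cover continues. Under Appendix 3, "before each study drug administration, the respiratory therapist should make sure that the research subject is on the lowest amount of oxygenation required". Risks of Active Study Drug promises oximetry at each dose escalation. Withdrawal criterion 1 stops the drug after a fall of 10 points or more to below 90% "within 15 minutes of drug administration, regardless of apparent relationship to coughing".
- **Blood pressure.** Cover is thinner. The reduction rule is confined to escalation. From Day 1 the coordinators record the flow-sheet value nearest before Dose 1, so no post-dose reading is specified for Day 8.

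Safety and tolerability are central aims of this trial, and dose intolerance is an outcome reported to the DSMB. An unintended rechallenge could expose patients and add avoidable events.

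**Working it through.** **Inputs.** Dose Rationale gives 6 µg per breath, a 36 µg start (6 breaths), steps of 3 breaths and a maximum of 72 µg (12 breaths). The Dosing Schedule gives Day 8 as 12 breaths every 6 hours, which is 4 doses. The Maintenance row states no interval. Every 4 hours (6 doses a day) is inferred from the escalation times and from the q4h reasoning in Dose Rationale.

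**Check of the plan's own figures.** 6 × 6 = 36 µg and 12 × 6 = 72 µg, both as stated. The middle level is 9 × 6 = 54 µg.

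**Single dose on Day 8, as written**

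| Failed at | Capped at | Day 8 dose | Change from tolerated dose | Against failed dose |
|---|---|---|---|---|
| 9 breaths | 6 breaths (36 µg) | 12 breaths (72 µg) | 72/36 = 2.00 (+100%) | 12 − 9 = 3 breaths above |
| 12 breaths | 9 breaths (54 µg) | 12 breaths (72 µg) | 72/54 = 1.33 (+33%) | 12 − 12 = 0, equal |

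For the 6-breath patient this is a rise of 6 breaths in one step, twice the 3-breath step allowed in escalation.

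**Daily total, maintenance to Day 8.** Day 8 is 72 × 4 = 288 µg for everyone.

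| Group | Maintenance q4h (assumed) | Ratio on Day 8 | Maintenance q6h (alternative) | Ratio on Day 8 |
|---|---|---|---|---|
| Cap 6 | 36 × 6 = 216 µg | 288/216 = 1.33 | 36 × 4 = 144 µg | 2.00 |
| Cap 9 | 54 × 6 = 324 µg | 288/324 = 0.89 | 54 × 4 = 216 µg | 1.33 |
| No cap | 72 × 6 = 432 µg | 288/432 = 0.67 | 72 × 4 = 288 µg | 1.00 |

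On the q4h reading, which the text supports better, the daily total rises only for the 6-breath cap. The single-dose result does not depend on the interval.

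**Which measure matters.** The plan judges oxygen intolerance dose by dose, in 15-minute windows after treatment. Dose Rationale reports plasma levels peaking at 10–15 minutes and falling quickly over the first hour. The single dose is therefore the relevant quantity, and a lower daily total does not remove the concern.

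**With the fix.** Limiting each row to the smaller of the printed dose and the tolerated dose gives, for Days 8–11, 6, 6, 4, 2 breaths (cap 6), 9, 6, 4, 2 (cap 9) and 12, 6, 4, 2 (no cap). Day 8 totals become 36 × 4 = 144, 54 × 4 = 216 and 72 × 4 = 288 µg. Against q4h maintenance, 144/216 = 216/324 = 288/432 = 0.67, the same one-third fall in every group.

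**How many patients.** This cannot be derived. The nearest figures, from long-term open-label studies cited in Dose Rationale, are 89% reaching 9 breaths and 42% reaching 12, so 11% and 58% did not. They come from another setting, and because 9 breaths was the target there, they are not intolerance rates.

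**The case against.** The strongest reply is that the table shows the course of a patient who reached 12 breaths. For that patient, Day 8 keeps the dose and lengthens the interval, so the natural equivalent for a capped patient is the tolerated dose every 6 hours. The heading of the phase, the step-down wording in Dose Rationale and the down-titration wording under Completion of Study Drug Administration all point that way. Dose Rationale makes escalation conditional on tolerability, and Minimization of Risks refers to dose reductions for adverse effects. Withdrawal criterion 2 stops the drug for intractable cough with worsening hypoxemia in any phase. Criterion 3 presupposes down-titration for hypotension and names no phase.

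Few patients can be affected. Thirty at 2:1 is about 20 on active drug. An affected patient must fail escalation, avoid withdrawal, still be in hospital on Day 8 and not have tapered early. The number may be zero.

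Much of this stands: no increase was intended, a sensible clinician would probably taper from the current dose, and the number at risk is small. But none of these texts sets the Day 8 dose for a capped patient, and the withdrawal criteria act only after an event. The table does print a number, therapists count breaths from it, and dosing may take place in any adult ICU or on any floor. Nor can the seven-day limit be read as covering all dosing, since the plan allows up to 12 days.

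**Conclusion.** The concern holds. Followed exactly, the written rule returns a 9-breath patient to the dose that failed (+33% per dose) and takes a 6-breath patient above it (+100% per dose). This is a wrong rule as printed, although clearly not the authors' intent. It should be corrected.

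The result rests on staff following the Day 8 row literally and on 6 µg per breath. It is a statement about single doses and should not be extended to daily exposure, which on the assumed q4h maintenance rises for the 6-breath cap (+33%) but falls for the 9-breath cap (−11%). The same question can arise before Day 8, because the entry row for an early taper is not stated. The Day 8 row has no bearing on the Day 2 and Day 7 primary endpoint; this is a patient-safety point affecting an unknown number of patients.

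**What to change.** Change the first Taper Down row to read: highest tolerated dose (maximum 12 breaths) every 6 hours. Add one sentence stating that no taper dose, whenever the taper starts, may exceed the patient's highest tolerated dose. Any further change to the Day 9–11 steps is for the clinical team.

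The cost is one table row and one sentence. Sample size, assessments and the primary analysis do not change.

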- 2) Acute onset need for 4 LPM or more of supplemental oxygen to maintain $PaO_2 > 60$ mmHg or arterial O_2 saturation > 90% by pulse oximetry.
- Acute unilateral pulmonary infiltrate/s on chest radiograph with no clinical evidence of left-sided heart failure. Bilateral infiltrates are acceptable as long as all other inclusion/exclusion criteria are met.

"Acute onset" is defined as follows: the duration of the hypoxemia criterion (#2) must be less than 96 hours and the chest radiograph criterion (#3) must be ≤ 28 days at the time of randomization. We acknowledge there is some difficulty determining absolute acuity with a 28 day window for the chest radiograph criterion, but this criterion is consistent with multiple NHLBI ARDSnet studies to date.

Patients must still meet inclusion criteria at the time of informed consent and randomization. Randomization is defined as the time that the IDS is contacted and informed about stratification of non-trauma and trauma patients. Patients that no longer meet eligibility criteria at the time of randomization are eligible to be re-screened if they meet inclusion criteria eligibility again.

Exclusion Criteria:

- 1) No consent/inability to obtain consent
- 2) Presence of pulmonary embolism
- 3) Known diffuse alveolar hemorrhage from vasculitis
- 4) Known pre-existing severe obstructive or restrictive lung disease (FEV 1 < 40% predicted, TLC < 50 % predicted) or need for long-term supplemental oxygen therapy
- 5) Known significant left ventricular systolic dysfunction with LVEF < 40% on echocardiogram.
- 6) Mean arterial pressure < 65 mmHg
- 7) Need for norepinephrine or dopamine dose > 12 mcg to maintain MAP > 65 mmHg
- 8) Severe chronic liver disease (Child-Pugh Score 11-15)

Measure	1 point	2 points	3 points	Units
Bilirubin (total)	<34 (<2)	34-50 (2-3)	>50 (>3)	μmol/l (mg/dl)
Serum Albumin	>35	28-35	<28	g/l
INR	<1.7	1.71-2.20	> 2.20	no unit
Ascites	None	Suppressed with medication	Refractory	no unit
Hepatic Encephalopathy	None	Grade I-II (or suppressed with medication)	Grade III-IV (or refractory)	no unit

- 9) Moribund patient not expected to survive 24 hours
- 10) QTc interval > 550 ms on screening bedside strip or electrocardiogram
- 11) Pregnancy or breast feeding (Women of childbearing potential, defined as < 60 years of age, will require pregnancy testing.)
- 12) Burns > 40% total body surface
- 13) Acute Neurological Disease (that may impair the ability to ventilate without assistance

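### The oxygen threshold in withdrawal item 2 is set in LPM, while Appendix 3 titrates high flow mainly by FiO2, so whether it is met can depend on device and reading; the hypoxemia terms also need reconciling

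*Combined protocol and SAP*

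**What the plan says.** **The stopping rule.** Item 2 under Premature Withdrawal from Treatment opens with a clinical condition, "Severe, intractable cough resulting in worsening hypoxemia and prolonged increase in" oxygen requirement. It then quantifies the rise: "Defined as an increase of more than 2LPM" of O2, closely tied in time to the cough. No FiO2 equivalent is given.

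**The oxygen ladder.** Entry requires an "Acute onset need for 4 LPM or more of supplemental oxygen" (Inclusion Criteria, item 2). Under Appendix 3, staff "titrate from their current nasal cannula flow rate in the following stepwise fashion: 4LPM / 5LPM /6LPM". Above 6 LPM, "we will utilize a High Flow Nasal Cannula with the flow rate of 20 to 50 LPM". On that device, "We will titrate the High Flow Nasal Cannula FiO2 in the following stepwise fashion: 50%, 60%, 70%, 80%, 90%, and 100" percent are the FiO2 steps, and liter flow is adjusted separately to patient need. The conversion table puts 4, 5 and 6 LPM at 36%, 40% and 44%.

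**The hypoxemia rules.** The text after the Dosing Schedule defines transient worsening hypoxemia as an SpO2 fall of 7% or more "within 15 minutes of treatment for no longer than 15 minutes not associated with coughing or exertion". The escalation hold in the same section refers only to worsening hypoxemia, with no definition. The taper rule is set on FiO2 (above 0.50). Withdrawal item 1 requires a fall of at least 10 percentage points, to below 90%, within 15 minutes of dosing.

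**The concern.** A stopping rule should order patients by the quantity it is meant to track, here the rise in oxygen need. Item 2 measures that rise in litres of flow, while the plan's own titration protocol changes scale when the patient changes device. The same clinical picture could then lead to opposite decisions, depending on the device in use and on how a member of staff reads the unit.

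Tolerability is a stated objective. Study discontinuation, intractable cough and worsening oxygenation are among the outcomes tabulated for safety and sent to the DSMB. With 30 patients randomised 2:1 (about 20 and 10), one patient classified differently moves an arm's rate by 1/20 = 5 or 1/10 = 10 percentage points.

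**Working it through.** The plan states no figure on this point that could be reproduced. The check sets item 2's threshold against the steps in Appendix 3.

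**Inputs.** Threshold: more than 2 LPM (withdrawal item 2). FiO2: 36%, 40% and 44% at 4, 5 and 6 LPM; 50% to 100% on high flow at 20 to 50 LPM (Appendix 3). Resting SpO2 target: 90-94% (Appendix 3). Assumptions of this check: room air is 21% oxygen, and conventional cannula flow is pure oxygen.

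**Step 1, literal reading (change in set flow).** The clinical conditions of item 2 are taken as present throughout.

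- 4 to 6 LPM: FiO2 44 − 36 = +8 points; flow 6 − 4 = +2 LPM. Not met, because the rule needs more than 2. No move within the 4/5/6 ladder can meet it.
- 6 LPM to high flow at 50%: FiO2 50 − 44 = +6 points; flow 20 − 6 = +14 to 50 − 6 = +44 LPM. Met.
- High flow 50% to 100%, flow unchanged: FiO2 +50 points; flow 0 LPM. Not met.
- High flow 20 to 25 LPM, FiO2 unchanged: FiO2 0 points; flow +5 LPM. Met.
- A patient weaned to 3 LPM (32%) who returns to 6 LPM: FiO2 44 − 32 = +12 points; flow +3 LPM. Met.

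So +6 points passes while +8 and +50 do not.

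**Step 2, reading the litres as pure oxygen.** Oxygen flow = total flow × (FiO2 − 0.21)/0.79.

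- High flow 50% to 60% at 20 LPM: 20 × 0.10/0.79 = +2.5 LPM. Met. At 50 LPM: 50 × 0.10/0.79 = +6.3 LPM. Met.
- High flow 50% to 100% at 20 LPM: 20 × 0.50/0.79 = +12.7 LPM. Met.
- 6 LPM to high flow 20 LPM at 50%: 20 × 0.29/0.79 − 6 = 7.3 − 6 = +1.3 LPM. Not met. At 50 LPM: 18.35 − 6 = +12.35, about +12.4 LPM. Met. The crossing point is (6 + 2) × 0.79/0.29 = 21.8 LPM.
- High flow 20 to 25 LPM at 50%: 5 × 0.29/0.79 = +1.8 LPM. Not met.
- 4 to 6 LPM: +2 LPM. Not met, as before.

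Several answers therefore reverse between the two readings, and nothing in the text chooses between them.

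**Step 3, desaturation.** From 90-94%, a fall of 7 to 9 whole points gives 81% (90 − 9) to 87% (94 − 7). That is below 90% but short of item 1's 10 points. If it lasts over 15 minutes it is also outside the transient definition. By phase:

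- Escalation: the hold may apply, through an undefined term.
- Maintenance (20 hours through Day 7): the hold is confined to escalation and the FiO2 rule to taper, so no numeric rule covers the fall unless another withdrawal item is met.
- Taper: the FiO2 rule applies if oxygen has to rise above 0.50.

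No action rule in any phase uses the defined transient term. Its 7% is also not labelled. Read as relative, it is 0.07 × 90 = 6.3 to 0.07 × 94 = 6.6 points, whereas item 1 says percentage points.

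**The case against.** The best defence is that item 2 does not stand alone. A change of device does not stop drug by itself: severe, intractable cough, worsening hypoxemia and a prolonged rise must all be present. A patient with all of these who has gone past 6 LPM is not an obvious false positive. Liter flow on high flow is also titrated, so a rise of more than 2 LPM can occur there, and the 0 LPM case holds only if flow is left unchanged. A patient on 4 LPM who needs more than 2 LPM extra moves to high flow and then passes the literal threshold. Item 1 applies on either device and regardless of cough, and items 4 and 5 stop drug for intubation or for BiPAP/CPAP.

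The hypoxemia gap is also limited. The escalation hold has no duration limit, Dose Rationale makes escalation depend on the absence of significant desaturation, and post-dose worsening of oxygenation is a reportable adverse event.

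All of this stands, and it rules out the stronger readings a reader might infer: that high-flow patients cannot meet item 2, that a device switch alone triggers withdrawal, or that a shorter desaturation has a defined action while a longer one has none. It does not remove the mismatch. The qualitative terms carry no threshold, adverse event reporting sets no dosing action, and items 4 and 5 do not register an FiO2 rise on high flow.

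On impact, the defence is partly right. The DSMB sections do not tie their cough and oxygenation counts to the 2 LPM figure. The 54% cough rate under Risk Assessment is for any cough, which the plan calls usually mild.

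**Conclusion.** The point holds in a limited form. The numeric part of item 2 is not on a scale that works for both devices in Appendix 3. Read literally, +6 FiO2 points can pass while +8 and +50 do not; read as pure oxygen, several of those answers change. Whether item 2 is met can therefore depend on device and reading rather than on oxygen need. This rests on the Appendix 3 conversion table, on the clinical conditions being present, and, for the second reading, on 21% room air and pure oxygen through the conventional cannula.

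Separately, the transient hypoxemia definition is not linked to any action, the escalation hold uses an undefined term, and the Maintenance Phase has no numeric rule for a fall of 7 to under 10 points lasting over 15 minutes.

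A reader might also infer bias between the arms. The documents do not support that: the same wording applies to both arms under blinding, and they give no estimate of how many patients would be affected. Sample size and the efficacy analysis do not depend on this point. It is a cheap correction to a stopping rule, below must-fix.

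**What to change.** Reconcile withdrawal item 2 with Appendix 3 so that its threshold is expressed on a scale valid on both devices, and state what the litres refer to if that unit is kept. The Appendix 3 conversion table already exists, and the taper rule is already written in FiO2.

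Reconcile the hypoxemia terms in the text after the Dosing Schedule with those under Premature Withdrawal from Treatment. State which rule uses the defined transient term, what worsening hypoxemia means in the escalation hold, whether 7% means percentage points, and what the plan intends for the Maintenance Phase. All thresholds and actions are for the sponsor to set; none is proposed here.

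The cost is protocol wording only, with no new measurement. The downside is that some patients may be classified differently. The Study Stopping Rules section suggests that enrollment has begun, so the amendment should record the date from which the revised wording applies.
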